8.3 Safety Laboratory Parameters

Laboratory chemistry and hematology data will be listed for each subject in the Safety Population with values outside the normal reference ranges flagged as low or high.

Descriptive statistics of each chemistry and hematology parameter will be presented for the Safety Population, showing the observed visit and change from Baseline to each visit value.

The number of patients with reported transaminases (AST, ALT, Alkaline phosphatase, total bilirubin) that are outside the defined ULN threshold multiples (see section 3.2.2) will be summarized showing the counts and percentages for Period 1 and Period 2 separately and for Period 1 and Period 2 combined, using the Safety Population.

Pharmacogenetic data (CYP2D6 genotyping at screening) will be listed for each subject in the Safety Population. Any incidences of polymorphisms (see section 3.4.5) will be summarized for the Safety Population.

A cross-tabulation will be displayed to show the agreement between the CYP2D6 genotyping status (PM, IM, EM, UM) and the phenotype status defined from the ratio of the CIS:PEX ratio (<0.4 , ≥ 0.4) from the Week 1 plasma levels (see section 3.3.1).

8.4 HbA1c

HbA1c data will be listed for each subject in the Safety Population with values outside the normal reference ranges flagged as low or high.

The change from Baseline to the end of Period 2 will be analyzed using an ANCOVA with a covariate of baseline HbA1c for the Completer Population.

The difference between the change from Baseline at the end of Period 1 compared to the change from Baseline at the end of Period 2 will be analyzed using an ANCOVA with a covariate of baseline HbA1c for the Completer Population.

The change from Baseline to the end of Period 1 will be analyzed using an ANCOVA with a covariate of baseline HbA1c for the Completer Population.

8.5 Vital Signs

Vital signs data from patients in the Safety Population will be presented in a data listing. The listing will identify the Baseline value, and present the visit value and change from Baseline to

each visit value, for each parameter. Values outside the thresholds indicated in section 3.2.4 will be identified on the listing.

Descriptive statistics of each vital signs parameter will be presented for the Safety Population, showing the observed visit and change from Baseline to each visit value. The number of patients who report a vital signs parameter outside the thresholds at any visit during Period 1, or Period 2 will be summarized using counts and percentages for the Safety Population.

Shift tables will be used to indicate the number of patients with systolic or diastolic blood pressure or heart rate values that changed status relative to the thresholds identified above (section 3.2.4) between Baseline and any vital signs assessment during each period.

8.6 ECG Parameters

All ECG data from patients in the Safety Population will be presented in a data listing. The listing will identify the Baseline value, and present the visit value and change from Baseline to each visit value, for each parameter. Each ECG parameter will be summarized using descriptive statistics for each assessment visit using the Safety Population.

The number of patients experiencing visit values or changes from Baseline within the ranges specified in section 3.2.5 will be summarized by counts and percentages for patients in the Safety Population.

Shift tables will be used to indicate the number of patients with QT or QTcF values or changes from Baseline values that changed status relative to the thresholds identified above (section 3.2.5) between Baseline and any ECG during each period.

The change from Baseline of the QTcF interval at the end of study-drug dosing Period 1 compared to the change from Baseline at the end of study-drug dosing Period 2 will be analyzed using an ANCOVA for the Safety Population.

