2.5 PERHEXILINE THOROUGH QT STUDY

PEX has MICE which might also predict a potential QT prolongation effect. Nevertheless, pro-arrhythmic effects have not been seen to any significant extent in its > 30 year clinical experience. The Australian Therapeutic Goods Administration label notes that the drug may be associated with QT prolongation and has been associated with a single report of TdP.

A thorough QT (TQT) study was done to establish the frequency and degree of PEX effects on the QT/QTcF interval. In that study PEX caused QT prolongation (ΔΔ QTcF of 15.3 and 22.8 msec at mean C_{max} of 278.6 and 677.9 ng/mL, respectively) within the plasma concentration ranges tested in this study. Most of the QTcF prolongation was the result of the ΔΔT_{peak-Tendc} at all timepoints up to and including 8 hours post-dosing. Subsequently the QTcF prolongation was the product of similar, combined effects of the ΔΔT_{peak-Tendc} and ΔΔJ-T_{peakc}. This suggests that PEX has mixed ion channel effects at relevant plasma levels, reducing the effect of hERG inhibition. PEX also had a mild effect on heart rate and AV nodal conduction indicating possible late sodium channel effect. PEX was well tolerated with few AEs and no serious adverse events (SAE); there were no pro-arrhythmic events seen during the study. In view of the QTcF prolongation, enhanced cardiac screening and monitoring for QT prolongation and arrhythmias will be included in this clinical study.

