4.3.2 QT Interval-Related Exclusion Criteria

- a. Personal history of congenital long QT syndrome, TdP, or drug-induced long QT
- b. On the basis of the mean of triplicate ECGs at screening or baseline:
 - i. QTcF > 500 msec if QRS ≤ 100 msec
 - ii. JTcF > 410 msec if QRS > 100 msec
- c. Serum potassium < 3.8 mEq/L (may be repeated up to two times during screening after attempts at medical management)
- d. Currently taking a medication with known risk of QT prolongation and TdP as listed in the “Known Risk of TdP” Risk Category on www.crediblemeds.org [Woosley and Romero].
- e. If possessing a pacemaker or Implantable Cardioverter Defibrillator (ICD), ventricular pacing > 10% of the time

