4.4.4 Dose-Adjustment for QTcF/JTcF Prolongation

Any dose adjustment instructions due to QTcF/JTcF prolongation will be at the direction of the ECG Core laboratory. Decisions to hold dosing until ECG Core Laboratory analysis is complete may be made at the site.

Dose adjustment for QTcF/JTcF prolongation (regardless of systemic PEX levels, unless the PEX levels and dose adjustment algorithm result in a dose reduction or discontinuation of a greater magnitude) will be done as described below for:

- a. Patients with a QRS interval \leq 100 msec WITH;
 - A prolonged QTcF $>$ 540 msec OR,
 - An increase in QTcF $>$ 75 msec over baseline AND QTcF $>$ 500 msec
- b. Whenever either the baseline or a subsequent ECG has a prolonged QRS $>$ 100 msec, changes in the JTcF will be used for all further dose-adjustment decisions throughout the remainder of the study for those patients. In a patient with a baseline or an on-study ECG showing a QRS interval $>$ 100 msec, the dose will be adjusted as described below IF;
 - The change from baseline in JTcF is $>$ 75 msec over baseline AND the JTcF interval is $>$ 410 msec OR,
 - An on-study JTcF interval is $>$ 450 msec

The dose of study drug for such patients will be stopped for 2 days and the daily dose subsequently reduced by 35 mg (for patients receiving \leq 105 mg) or 70 mg (for patients receiving \geq 140 mg) and restarted only if the QTcF/JTcF measurement has fallen back into the acceptable range for continued dosing. If the QTcF/JTcF measurement has NOT fallen back into the acceptable range after stopping drug for 2 days, the process of holding study drug and rechecking the ECG every 2 to 3 days will continue until the QTcF or JTcF limits are not exceeded and at which time study drug may be restarted at the reduced dose. The dose of study drug will not be increased any further during the remainder of the study (neither Period 1 or Period 2) if a dose reduction for QTcF or JTcF prolongation is required.

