For each ECG parameter (RR, PR, QRS, QT, TP, T-wave, QTcF, JTcF) within each trace, a mean of the three complexes was to be derived. A mean of the three traces was then to be derived from the mean of the three complexes. This mean (of traces) of the mean (of complexes) will be presented in the ECG listings and used in the ECG descriptive statistics and analyses. Individual complexes will be available in the SDTM and ADaM datasets only and will not be presented in study listings.

ECG Corelab will also provide a Global RR value for the whole ECG trace. From this Global RR, statistical programming will derive ECG heart rate:

$$HR = 60 / [Global\ RR / 1000]$$

In addition to the above measurements, ECG Corelab was to provide an overall interpretation of the ECG. ECG traces were also to be made available to the study site Investigator, who would provide their overall interpretation and an indication of the clinical significance of any findings.

Changes in each of the ECG parameters from Baseline to each post-Baseline will be derived. The last ECG assessment prior to starting study medication will be regarded as Baseline (this will usually be the Day 1 assessment).

Assessment values or changes from Baseline that are outside the thresholds presented below will be identified in an analysis dataset by electronic programming for reporting purposes.

	Thresholds
QT (msec)	>450 >480 >500
Changes in QT (msec)	>30 >60
QTcF (msec)	>450 >480 >500
Changes in QTcF (msec)	>30 >60

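### ECG outlier and shift tables use only QT/QTcF cut-offs, although the protocol judges patients with QRS above 100 msec on JTcF, and none of the protocol's own QTcF/JTcF action limits is counted

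*SAP*

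**What the plan says.** **Protocol.** Section 4.3.2 sets two alternative interval limits for exclusion. QTcF above 500 msec applies when QRS is at most 100 msec. Otherwise the criterion is "JTcF > 410 msec if QRS > 100 msec", with no QTcF ceiling. Section 4.4.4 carries the split into treatment: once a baseline or later ECG shows QRS above 100 msec, "changes in the JTcF will be used for all further dose-adjustment decisions throughout the remainder of the study for those patients". Its action limits are:

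- QRS at most 100 msec: QTcF above 540, or a QTcF rise above 75 with QTcF above 500.
- QRS above 100 msec: JTcF above 450, or a JTcF rise above 75 with JTcF above 410.

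Section 8.1.2 makes ECG abnormalities in Period 1 versus Period 2 part of a secondary endpoint, and names the QTcF change at the end of each period as another. Section 8.1.3 makes the same comparison for other ECG variables exploratory.

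**SAP.** Section 3.2.5 derives JTcF as QTcF minus QRS and averages it like the other intervals. Its threshold table covers QT and QTcF only: values ">450 >480 >500" and changes above 30 and 60 msec. Section 8.6 ties the outlier counts to that table ("The number of patients experiencing visit values or changes from Baseline within the ranges specified in section 3.2.5 will be summarized by counts and percentages"). It does the same for the shift tables: "Shift tables will be used to indicate the number of patients with QT or QTcF values or changes from Baseline values that changed status". The formal period comparison in 8.6 is on QTcF alone. JTcF appears only in listings and in descriptive statistics by visit.

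**The concern.** The trial uses one measure to decide whether a wide-QRS patient may enter and stay on dose, and another to tabulate ECG outliers in that patient. Two things follow. The highest absolute category may already be occupied at baseline in wide-QRS patients. And in patients of any QRS width, the limits that trigger a hold and reduction under the protocol cannot be read off any planned table.

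ECG response is a secondary objective, and the study compares two exposure ranges to choose a regimen for Phase 3. The number of patients who met the trial's own QTcF/JTcF limits in each range is therefore a result a reader will look for. As planned, it would have to be assembled from listings.

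**Working it through.** The plan states no figure to reproduce here. The check is arithmetic on the SAP's definition JTcF = QTcF − QRS, so QTcF = JTcF + QRS. All values are in msec.

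**Step 1. Highest QTcF allowed at entry when QRS is above 100.** The limit JTcF ≤ 410 gives QTcF ≤ 410 + QRS. Baseline QTcF exceeds 500 when JTcF exceeds 500 − QRS. The JTcF limit of 450 corresponds to QTcF = 450 + QRS.

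| QRS | Highest entry QTcF (410 + QRS) | Baseline JTcF above which QTcF > 500 (500 − QRS) | QTcF at JTcF 450 (450 + QRS) |
|---|---|---|---|
| 101 | 511 | 399 | 551 |
| 110 | 520 | 390 | 560 |
| 120 | 530 | 380 | 570 |
| 140 | 550 | 360 | 590 |

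At QRS 120, a baseline JTcF above 380 and up to 410 puts the patient above 500 before the first dose. The SAP has no higher absolute category to move into. With QRS at most 100, QTcF above 500 is excluded at entry, so the top category starts empty and works as intended.

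**Step 2. Can the tables separate patients who met an action limit from those who did not?** Each pair below uses assumed, eligible values with QRS unchanged. Both members get identical SAP entries.

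| QRS | QTcF, baseline to on-study | JTcF, baseline to on-study | SAP entry | Protocol limit met |
|---|---|---|---|---|
| 140 | 540 to 575 (+35) | 400 to 435 | >500 to >500; change >30 | none |
| 140 | 540 to 595 (+55) | 400 to 455 | >500 to >500; change >30 | JTcF >450 |
| 120 | 440 to 516 (+76) | 320 to 396 | ≤450 to >500; change >60 | none (JTcF not above 410) |
| 120 | 440 to 531 (+91) | 320 to 411 | ≤450 to >500; change >60 | JTcF rise >75 with JTcF >410 |
| 90 | 495 to 530 (+35) | not used | >480 to >500; change >30 | none |
| 90 | 495 to 545 (+50) | not used | >480 to >500; change >30 | QTcF >540 |
| 90 | 435 to 505 (+70) | not used | ≤450 to >500; change >60 | none |
| 90 | 430 to 506 (+76) | not used | ≤450 to >500; change >60 | QTcF rise >75 with QTcF >500 |

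None of the four limits can be isolated from the planned categories.

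**Step 3. What do the change cut-offs still catch?** Take a patient with wide QRS at baseline and QRS unchanged. Passing JTcF 450 from an entry value of at most 410 means a rise above 40, so the patient is counted under QTcF change >30. A JTcF rise above 75 is counted under >60. Worsening is therefore registered.

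If QRS moves, change in QTcF = change in JTcF + change in QRS. Two assumed cases:

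- QRS 110 to 130, JTcF 380 to 395: QTcF goes 490 to 525. The rise of 35 is counted under >30, although JTcF rose by only 15.
- QRS 130 to 115, JTcF 380 to 415: QTcF goes 510 to 530. The rise of 20 is not counted, although JTcF rose by 35.

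**The case against.** Much can be said for the plan as written.

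- The QTcF change cut-offs work whatever the baseline. A reader might infer that the tables hide worsening in wide-QRS patients. Step 3 shows that they do not; only the absolute categories lose their use.
- JTcF and QRS are listed with baseline, visit value and change. SAP 5.4 puts the maximum in every descriptive summary, so the highest JTcF at each visit will be printed. With about 33 patients, the limits can be counted by hand. A reader might infer that the report could never say how many patients met them, and that goes too far. What is missing is a pre-specified count.
- The SAP 8.6 shift tables compare baseline with any ECG in the period, so a peak before a hold or reduction does enter them.
- The end-of-period QTcF comparison is the endpoint that protocol 8.1.2 names. A reader might infer that it is biased, because a patient who met a limit earlier has since been held and reduced, and under 4.4.4 "The dose of study drug will not be increased any further during the remainder of the study". The documents do not support a figure for this. They do not say how many patients would be managed, in which period, or by how much their QTcF would fall. ECGs taken after dose adjustment also reflect the titrated regimen under study.
- A wide-QRS patient starting above 500 msec may be rare or absent in this sample.

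All of these stand as limits on the point. None supplies a JTcF category or a count of the action limits. The outlier-count sentence in SAP 8.6 also names no period, whereas the vital-signs count in 8.5 does.

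**Conclusion.** The point holds as a reporting gap of minor to moderate weight. The SAP's categories do not match the measure the protocol uses when QRS exceeds 100 msec, and all four action limits in protocol 4.4.4 go uncounted. The top QTcF category can be occupied at entry in wide-QRS patients: entry QTcF can reach 520, 530 or 550 msec at QRS 110, 120 or 140.

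The arithmetic rests only on the SAP's JTcF definition and the protocol's limits; the patient profiles are illustrations. The number of patients affected cannot be estimated, because the documents give no baseline QRS or JTcF distribution. The point does not show bias in the QTcF period comparison, and no clinical limit is questioned.

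**What to change.** Revise SAP 3.2.5 and 8.6, which SAP section 1 permits before database lock:

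1. For each period, tabulate the number and percentage of patients meeting each existing protocol 4.4.4 limit at any ECG. Apply the protocol's rule ECG by ECG: QTcF limits until the first QRS above 100 msec, JTcF limits from then on.
2. Give the outlier and shift tables by QRS group. Use the QTcF categories where QRS stayed at or below 100 msec. Otherwise use JTcF above 410 and above 450, with changes above 30, 60 and 75 msec. State that the outlier counts are by period.
3. Keep the end-of-period QTcF comparison as the protocol names it. Repeat it on JTcF, as part of the exploratory comparison of other ECG variables in protocol 8.1.3.
4. Optionally, add a supportive analysis of each patient's largest change per period. Two-weekly ECGs make it possible, but it answers a different question from the named endpoint.

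The cost is a few table rows and one repeated model on variables already derived. The downside is small counts in the QRS groups, so these tables should be read as description.

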8.1.2 Secondary Endpoints

The secondary endpoints of the study are:

- The change from baseline of VO₂MAX at the end of study-drug dosing Period 1 compared to the change from baseline at the end of study-drug dosing Period 2.
- An evaluation of the change in VO₂MAX at the end of study-drug dosing Period 1 compared to baseline will be performed.
- The change from baseline of the QTcF interval at the end of study-drug dosing Period 1 compared to the change from baseline at the end of study-drug dosing Period 2

- The change from baseline at the end of study-drug dosing Period 2 in the Six-Minute Walk Test (6MWT) and change from baseline at the end of study-drug dosing Period 1 compared to the change from baseline at the end of study-drug dosing Period 2
- Safety data (AEs, ECG abnormalities, routine laboratory safety test of blood, vital signs, and concomitant medication and patient withdrawals) during study-drug dosing Period 1 compared to study-drug dosing Period 2

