8.1.3 Exploratory Endpoints

Exploratory endpoints are:

- Change from baseline of other ECG variables at the end of study-drug dosing Period 1 compared to the change from baseline at the end of study-drug dosing Period 2
- Change from baseline of HbA1c at the end of study-drug dosing Period 1 compared to the change from baseline at the end of study-drug dosing Period 2

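### SAP 8.6 counts ECG abnormalities for QT/QTcF only and compares only QTcF between periods, so two protocol ECG endpoints are not fully delivered

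*SAP*

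**What the plan says.** **Protocol endpoints.** Protocol 8.1.2 contrasts the two dosing periods on a secondary endpoint that begins "Safety data (AEs, ECG abnormalities, routine laboratory safety test of blood, vital signs". In that list ECG abnormalities stand apart from AEs, and the QTcF change has its own bullet. Protocol 8.1.3 has an exploratory endpoint that begins "Change from baseline of other ECG variables at the end of study-drug dosing Period 1 compared to the change from baseline"; its comparator is Period 2.

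**What is collected.** Under SAP 3.2.5 the core laboratory reports RR, PR, QRS, QT and T-wave measures, and QTcF and JTcF are derived. In addition, "ECG Corelab was to provide an overall interpretation of the ECG", and the investigator gives an interpretation with a judgement of clinical significance.

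**What is tabulated.** SAP 3.2.5 says "Assessment values or changes from Baseline that are outside the thresholds presented below will be identified in an analysis dataset by electronic programming". The limits that follow are for QT and QTcF only. SAP 8.6 then plans:
- a listing of all ECG data;
- descriptive statistics for each parameter at each visit;
- counts against the SAP 3.2.5 limits, with no mention of period;
- shift tables within each period, introduced by "Shift tables will be used to indicate the number of patients with QT or QTcF values or changes from Baseline values that changed status";
- one between-period ANCOVA, for QTcF.

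**The concern.** If the SAP is followed exactly, the clinical study report will contain no between-period comparison of any ECG variable except QTcF. It will also contain no ECG-based count of abnormalities other than QT/QTcF. SAP 12, which lists departures from the protocol's analyses, does not say that either item was dropped, so the omission looks unintended.

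The protocol itself gives reasons to look beyond QTcF. Section 2.5 reports from the thorough QT study that "PEX also had a mild effect on heart rate and AV nodal conduction", and it announces enhanced monitoring for arrhythmias as well as for QT prolongation. Section 4.4.4 makes JTcF, not QTcF, the deciding measure for a patient once QRS exceeds 100 msec. For those patients, the interval that the protocol relies on has no reporting category in the SAP.

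**Working it through.** No planned figure is at issue, so the check sets each promised item beside its planned output.

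| Item | Source | Planned output | Gap |
|---|---|---|---|
| QT/QTcF limits | SAP 3.2.5 | Counts; shift tables per period (SAP 8.6) | Counts not stated to be by period |
| QTcF, Period 1 vs 2 | Protocol 8.1.2 | ANCOVA (SAP 8.6) | None on this point |
| Other ECG variables, Period 1 vs 2 | Protocol 8.1.3 | By-visit descriptive statistics | No between-period comparison |
| ECG interpretations | SAP 3.2.5 | Listing | No count, shift or by-period table |
| PR, QRS, JTcF outliers | Parameters in SAP 3.2.5 | n, mean, SD, median, minimum, maximum by visit (SAP 5.4, 8.6) | No category or count |
| HbA1c, Period 1 vs 2 | Protocol 8.1.3 | ANCOVA (SAP 8.4) | None on this point |

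**Extent.** The SAP 3.2.5 limits are three for QT, two for change in QT, three for QTcF and two for change in QTcF: 3 + 2 + 3 + 2 = 10. None concerns PR, QRS or JTcF. SAP 3.2.5 averages eight parameters over complexes and traces (RR, PR, QRS, QT, TP, T-wave, QTcF, JTcF), and one of the eight is compared between periods.

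**Comparison within the SAP.** HbA1c is the only other exploratory endpoint in Protocol 8.1.3, and SAP 8.4 gives it an explicit Period 1 vs Period 2 analysis. The laboratory and vital-sign threshold counts (SAP 8.3, 8.5) are stated by period. The ECG count sentence is the exception. SAP 8.3 and 8.5 also say that change from Baseline is summarized, and the SAP 8.6 sentence on descriptive statistics does not.

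**The adverse event route.** SAP 8.2 tabulates TEAEs by preferred term for Period 1, Period 2, both combined and Follow-up. The AE definition in Protocol 7.1 is wide enough to include an ECG sign. However, Protocol 7.12 asks only that significant ECG worsening be recorded in the medical record. An abnormal interpretation that nobody enters as an AE therefore appears in the listing and in no table, unless it coincides with a QT/QTcF limit.

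**Why summary statistics do not replace a count (illustration).** The documents give no SD for PR, so the inputs are assumed.
1. One patient of 33 gains 40 to 80 msec and the others do not change. The mean shift is 40/33 = 1.2 to 80/33 = 2.4 msec.
2. Two patients of 30 gain 60 msec and 28 do not change. The mean shift is 2 × 60/30 = 4 msec.
3. The SD in that scenario is √[(2 × 56² + 28 × 4²)/29] = √(6720/29) = 15.2 msec.
4. The 95% CI is 4 ± 2.045 × 15.2/√30 = 4 ± 5.7, that is -1.7 to 9.7 msec. It includes zero, while a count would show 2/30 = 6.7%.

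The visit maximum might reveal such a patient. It would not say how many patients were affected, or whether the long interval was already present at Baseline.

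**The case against.** The strongest reply is that most of the clinically important ground is covered elsewhere.
- An arrhythmia or conduction disorder reported as an AE is counted by period, with further tables by severity and for drug-related events (SAP 8.2).
- The descriptive statistics include SD, median, minimum and maximum (SAP 5.4), so an extreme PR or QRS can show.
- Vital-signs heart rate has limits, counts for each period and shift tables (SAP 3.2.4, 8.5).
- All ECG data are listed with Baseline and change. The Study Monitoring Team, which includes an independent cardiologist, reviews ECG listings about every two months (Protocol 4.8).
- With about 33 patients in one arm, a listing is a workable way to show sporadic findings.
- The thorough QT study called the AV-nodal effect mild and saw no pro-arrhythmic events (Protocol 2.5).

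All of this is correct, and it limits the point. A reader might infer that new arrhythmias and conduction changes appear in no table, or that PR is reported only as a mean. The AE tables and SAP 5.4 contradict both readings. It would also be wrong to call heart-rate outliers uncounted, or to say that the shift tables ignore period.

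Three gaps remain. The exploratory comparison in Protocol 8.1.3 has no analysis. ECG abnormalities that are neither QT/QTcF nor reported as AEs have no count, although the protocol lists ECG abnormalities separately from AEs. A listing and a by-visit maximum give neither a number of patients nor a Period 1 vs Period 2 contrast.

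**Conclusion.** The point holds as a gap in planned reporting. One exploratory endpoint (other ECG variables, Period 1 vs Period 2) has no comparison planned. One component of a secondary safety endpoint (ECG abnormalities) is covered only for QT/QTcF, apart from what reaches the AE tables. The collected interpretations have no table, JTcF has no reporting category despite its role in the protocol, and the period split of the threshold counts is unstated.

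The conclusion rests on the text of Protocol 7.1, 7.12, 8.1.2 and 8.1.3 and SAP 3.2.5, 5.4, 8.2, 8.6 and 12. It does not depend on the PR illustration, whose inputs are assumed. How many findings would go uncounted cannot be estimated from the documents, because it depends on how often sites enter ECG findings as AEs.

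A reader might also infer that patients are less well protected during the trial. The documents do not support that: ECG data are reviewed during the study, and the dose-adjustment rules operate independently of these tables. The primary endpoint is unaffected. The change should be made, but it is a matter of complete reporting.

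**What to change.** Amend SAP 8.6 before database lock, which SAP 1 allows. For the Safety Population, descriptive only:

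1. **Interpretations.** For Period 1, Period 2 and Follow-up, count patients with a new abnormal, and a new clinically significant, ECG interpretation not present at Baseline. Show core laboratory and investigator readings separately.
2. **Between-period comparison.** For PR, QRS, RR/ECG heart rate, JTcF and the other reported ECG variables, give the within-patient difference in change from Baseline, Period 2 minus Period 1, with a 95% CI. Since (P2 - Baseline) - (P1 - Baseline) = P2 - P1, this uses patients with both end-of-period ECGs, and their number should be shown. Leave PR out where it cannot be measured, for example in atrial fibrillation, because Protocol 4.2.2 admits patients with the chronic form.
3. **Existing counts.** State that the QT/QTcF threshold counts are by period.
4. **Outlier categories.** Add reporting categories for PR, QRS and JTcF, with cut-offs set by the sponsor before database lock, and count findings as new relative to Baseline. The QRS value of 100 msec in Protocol 4.4.4 is a switch between correction measures. Patients above it are eligible under Protocol 4.3.2, so a raw count would mix old findings with new ones.

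These are reporting categories only and change no clinical rule. The cost is SAP wording and a few more descriptive tables from data already collected, with no new procedure. The downside is more output without formal testing, and it should be labelled as such.
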